5.2.3.3 Rescue Therapy (LCIG Treatment Group Only)

After NJ and/or PEG-J placement, subjects randomized to LCIG should fill a prescription provided by the Investigator for oral LC-IR tablets in case oral rescue therapy is needed. Once LCIG treatment has been initiated, the prescribed oral LC-IR rescue tablets should only be used during scheduled LCIG use (16-hour infusion) in case of serious medical needs such as the rapid deterioration of motor symptoms that does not respond to an extra dose of LCIG. The subject should be instructed to record all oral levodopa tablets on the Subject Dosing Diary on the assigned days.

[figure not shown]
5.2.3.4 Post Infusion Night Time Therapy (LCIG Treatment Group Only)

Those subjects randomized to the LCIG Treatment group will be permitted to selfadminister their typical night-time regimen of oral LC-IR or levodopa-carbidopa continuous-release (LC-CR) following the daily discontinuation of the 16-hour infusion, only if they were taking this during the 30 day stable medication period during screening and the dose must remain unchanged. The Investigator will provide a prescription for the doses of oral LC-IR or LC-CR that the subject takes on a regular nightly basis. After the nightly discontinuation of LCIG treatment drug administration, levodopa-DOPA decarboxylase inhibitor (DDI) tablets or similar such as Levodopa + carbidopa = Sinemet, LD + CD + entacapone = Stalevo, Levodopa + Benserazide = Madopar may be taken up to 2 hours (for oral LC-IR) or 4 hours (for oral LC-CR) prior to the administration of the next morning dose of LCIG and should not be counted as rescue. The subject should record all oral levodopa-carbidopa tablets on the Subject Dosing Diary on the assigned days.

Those subjects randomized to the OMT group will remain on their normal, stable nighttime regimen if applicable.

5.2.4 **Contraception Recommendations and Pregnancy Testing**

If female, subject must be either postmenopausal defined as:

• Age > 55 years with no menses for 12 or more months without an alternative medical cause.

• Age < 55 years with no menses for 12 or more months without an alternative medical cause AND an FSH level > 40 IU/L.

OR

- Permanently surgically sterile (bilateral oophorectomy, bilateral salpingectomy or hysterectomy).
- Practicing at least one of the following methods of birth control, on Study Day 1 (or earlier) through at least 30 days after the last dose of study drug.
 - Combined (estrogen and progestogen containing) hormonal contraception (oral, intravaginal, transdermal) associated with the inhibition of ovulation, initiated at least 1 month prior to Study Day 1.
 - Progestogen-only hormonal contraception (oral, injectable, implantable) associated with inhibition of ovulation, initiated at least 1 month prior to Study Day 1.
 - o Bilateral tubal occlusion/ligation.
 - Vasectomized partner(s), provided the vasectomized partner has received medical assessment of the surgical success and is the sole sexual partner of the women of child bearing potential (WOCBP) trial participant.
 - o Intrauterine device (IUD).
 - Intrauterine hormone-releasing system (IUS).
 - Progestogen-only oral hormonal contraception, where inhibition of ovulation is not the primary mode of action, initiated at least 1 month prior to Study Day 1.
 - O True abstinence: Refraining from heterosexual intercourse when this is in line with the preferred and usual lifestyle of the subject (periodic abstinence [e.g., calendar, ovulation, symptothermal, post-ovulation methods] and withdrawal are not acceptable).

If male subject must be surgically sterile (vasectomy with medical assessment confirming surgical success) or have a female partner who is postmenopausal or permanently sterile (bilateral oophorectomy, bilateral salpingectomy or hysterectomy), OR if sexually active with female partner(s) of childbearing potential must agree from Study Day 1 through 4 weeks after the last dose of study drug to practice contraception with:

- Condom use.
- True abstinence: Refraining from heterosexual intercourse-when this is in line with the preferred and usual lifestyle of the subject. (Note: Periodic abstinence [e.g., calendar, ovulation, symptothermal, post-ovulation methods] and withdrawal are not acceptable).
- Additionally, male subject agrees not to donate sperm from Study Day 1 through 4 weeks after the last dose of study drug.

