1, 6, 7, 9, 15 – 18, 24, 25	To reduce the risk to subjects or others and/or to exclude underlying conditions that would compromise the ability to make causality assessments relative to LCIG treatment for safety events
5, 8, 10 – 14, 19, 22 – 23	To ensure safety of the subjects throughout the study
2-4, 20-21, 28	To exclude, or to minimize, the number of medications or other factors that could interfere with the LCIG treatment, or could add unnecessary variance or bias to safety evaluations

Christian Cel/Carbidopa Levodopa Enteral Suspension M15-535 Protocol Amendment 1 EudraCT 2016-001403-23

26 - 27

The impact of LCIG treatment on pregnancies and lactation is unknown

5.2.3 **Prior and Concomitant Therapy**

Any medication or vaccine (including over-the-counter or prescription medicines, vitamins and/or herbal supplements) that the subject is receiving from 30 days prior to signing the Informed Consent Form, or receives during the study, must be recorded along with the reason for use, date(s) of administration including start and end dates, and dosage information including dose, route and frequency.

The AbbVie TA MD should be contacted if there are any questions regarding concomitant or prior therapies.

5.2.3.1 **Prior Therapy (Prior to Randomization)**

All medications taken by the subject during the study and from 30 days prior to signing the Informed Consent Form are to be recorded in the eCRF.

5.2.3.2 **Concomitant Therapy**

All changes to concomitant medications must be carefully documented on the Concomitant Medication eCRF.

Allowable Medications

Anti-Parkinsonian Medications

The following classes of anti-Parkinsonian medications will be allowed during the study:

Levodopa formulations

- For the OMT group, all levodopa formulations are allowed
- For the LCIG treatment group:

- o levodopa formulations can only be used at nighttime (the 8 hours when the pump is not in use) or as rescue medication
 - long-acting levodopa formulations can only be used at nighttime (at least 4 hours prior the next day's morning dose)
 - short-acting levodopa formulations with the exception of formulations containing entacapone can only be used at nighttime (at least 2 hours prior to the next day's morning dose) or as rescue medication

Dopamine agonists (not including apomorphine continuous infusion or PRN injection)

MAO-B inhibitors

Anti-cholinergics

Amantadine –

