As an exception, subjects in both groups who take amantadine at the randomization visit (V3) must not discontinue this treatment and are required to continue this treatment for the entire study duration with the regimen kept stable unless the Investigator decides that it is medically indicated to discontinue this treatment. If subjects do not take amantadine at the Visit 1 (Screening Visit 1), this treatment must not be initiated during the entire study duration.

General Requirements

Screening to Visit 3: All anti-Parkinson's disease medications must be stable* for at least 30 consecutive days prior to V3 baseline assessments.

*A stable regimen is defined as no changes to the frequency of administration, dose of administration or total daily dose.

Randomization to End of Treatment Period:

- OMT Group: all anti-PD medications should remain stable from randomization to the Week 12 visit and study assessments unless medically indicated.
- LCIG treatment Group: Those subjects randomized to LCIG treatment must discontinue all other anti-PD medications other than amantadine (e.g., dopamine agonists, COMT-inhibitors, MAO-B inhibitors, anticholinergies, and subcutaneous apomorphine, etc.) prior to LCIG initiation on Day 1 (V4); these medications should be tapered off according to their individual package insert, and at the discretion of the Investigator, over a period of up to 14 days. With the exception of apomorphine, levodopa containing formulations or amantadine (see next paragraph), these medications may be restarted if indicated by the subject's individual condition, but not within the first 28 days after the PEG placement procedure.

As an exception, subjects in both groups who take amantadine at the randomization visit (V3) must not discontinue this treatment and are required to continue this treatment for the entire study duration with the regimen kept stable unless the Investigator decides that it is medically indicated to discontinue this treatment. If subjects do not take amantadine at the Visit 1 (Screening Visit 1), this treatment must not be initiated during the entire study duration.

Anti-PD medications should only be adjusted if medically indicated

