All medication taken by the subject during the study (from signing the Informed Consent form through post-study follow-up) is to be recorded on the appropriate eCRF, except for study drug for subjects randomized to LCIG treatment. All changes to concomitant medications, this includes all medications taken by subjects randomized to OMT, must be carefully documented on the Concomitant Medication eCRF.

Medications for Management of Dyskinesia (OMT Treatment Group)

All medications used for the management of dyskinesia must be stable for at least 30 consecutive days before the Randomization visit (V3). These medications should then also remain stable for the duration of the study.

The Investigator can make modifications to these medications or additional medications if medically indicated after discussion with the AbbVie TA MD.

Required Concomitant Medication, Antibiotics

The use of prophylactic antibiotics is required prior to PEG-J procedure. At minimum, a single dose of a 1st or 3rd generation cephalosporin (or an antibiotic with similar coverage) must be administered approximately 30 minutes prior to the PEG-J procedure.

Prohibited Medications (OMT and LCIG Treatment Groups)

The following medications (not comprehensive) are prohibited during the study.

Table 3. **Prohibited Medications and Treatments**

Antipsychotics

Both typical and atypical antipsychotics (except quetiapine and clozapine), including but not

limited to:

Aripiprazole

Fluphenazine

Haloperidol

Perphenazine

Pimozide

Thiothixene

Trifluoperazine

Loxapine

Molindone

Chlorpromazine

Mesoridazine

Thioridazine

Olanzapine

Risperidone

Ziprasidone

Depot neuroleptics

Antiparkinsonian

Apomorphine (PRN injection or continuous infusion)

Levodopa-carbidopa-entacapone (LCIG

treatment group only)

Antihypertensives

Centrally acting (including but not limited to reserpine, α-methyldopa, clonidine)

Cinnarizine

Flunarizine

Procedures

Neurosurgical procedure for the treatment of

Parkinson's disease

Benzodiazepines

Long acting benzodiazepines

Psychostimulants or Sympathomimetics

Psychostimulants (amphetamine,

dextroamphetamine, methylphenidate, pemoline,

Weight loss agents (phentermine, sibutramine)

Anticonvulsants

Barbiturates (such as phenobarbital, primidone)

Hydantoins (phenytoin, fosphenytoin)

Succinimides (ethosuximide)

Others (felbamate, lamotrigine, tiagabine, topiramate, carbamazepine and valproic acid)

Cognition:

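### Section 5.2.3.4 lets LCIG subjects take levodopa-carbidopa-entacapone at night although Table 3 prohibits it in that arm; the allowed-class list also omits COMT inhibitors

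*Protocol*

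**What the plan says.** Night-time treatment in the LCIG arm is governed by several Protocol texts.

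- **Section 5.2.3.4 (LCIG group only).** It opens by letting subjects keep their usual night-time LC-IR or LC-CR if they took it during "the 30 day stable medication period during screening and the dose must remain unchanged". Two sentences later, when giving the interval before the morning dose, it lists example products: "LD + CD + entacapone = Stalevo, Levodopa + Benserazide = Madopar may be taken up to 2 hours".
- **Section 5.2.3.2, Table 3.** The table is introduced with "The following medications (not comprehensive) are prohibited during the study". Its antiparkinsonian entries include "Levodopa-carbidopa-entacapone (LCIG" treatment group only).
- **Section 5.2.3.2, allowable levodopa for the LCIG group.** "short-acting levodopa formulations with the exception of formulations containing entacapone can only be used at nighttime" or as rescue.
- **Section 5.2.3.2, from randomization to end of treatment.** LCIG subjects "must discontinue all other anti-PD medications other than amantadine (e.g., dopamine agonists, COMT-inhibitors, MAO-B inhibitors" and others) before the first infusion. The Synopsis (Treatment Period) and Section 5.1.2.2 say the same.
- **Restart rule, same three places and SAP Section 4.2.** In the wording of 5.2.3.2: "With the exception of apomorphine, levodopa containing formulations or amantadine (see next paragraph), these medications may be restarted" if the subject's condition calls for it, but not in the first 28 days.

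**The concern.** The night-time permission and the Table 3 prohibition are both written for the LCIG arm, concern the same product, and say opposite things. The Table 3 entry is the only one in that table marked as applying to one arm, so it looks deliberate. A site that turns to 5.2.3.4 for night dosing finds the tablet named as acceptable. A site that checks Table 3 finds it banned. The first site would give a drug the protocol prohibits, and the second would refuse one the protocol permits. What an LCIG subject may take overnight is part of the treatment under comparison, so it should have one definition.

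The second, smaller matter is that the list of allowed drug classes does not mention COMT inhibitors, while other text assumes that subjects may be taking them.

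**Working it through.** The plan gives no figure on this point, so the check is a comparison of texts.

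**1. Can 5.2.3.4 and Table 3 both hold?** Three ways of reconciling them were tried.

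- *Table 3 means daytime only.* Its introduction covers the whole study and gives no time of day.
- *The opening of 5.2.3.4 limits the section to LC-IR and LC-CR.* That is a fair reading of the opening sentence. The later sentence nevertheless extends to similar products and names this one, so the permission is still on the page.
- *The allowed list rescues the tablet.* Taken alone, the exception for entacapone formulations is awkwardly placed and could be parsed as lifting the night-only limit. Beside the Table 3 ban, the sensible reading is that these formulations fall outside permitted night-time and rescue use. It then agrees with Table 3.

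None of the three lets both texts stand.

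**2. Does the stop-and-restart rule bring the tablet back?** No. Entacapone is the COMT inhibitor in the tablet, and COMT inhibitors stop before LCIG starts. The restart rule excepts levodopa-containing formulations, and this tablet is one.

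**3. Does any other text settle it?**

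- Section 5.1.2.2 (LCIG Initiation and Titration) gives the same 2-hour and 4-hour intervals without naming an entacapone product.
- SAP Section 8.4 describes only levodopa-carbidopa continuing at night. It is a descriptive sentence in a dose section and omits the amantadine exception, so it carries little weight.
- Appendix E (list of changes) does not touch the matter, and SAP Section 12.0 declares no change from the protocol.
- No statement was found of which section prevails.

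**4. COMT inhibitors as a class.** The list in 5.2.3.2 begins "The following classes of anti-Parkinsonian medications will be allowed during the study" and names levodopa formulations, dopamine agonists, MAO-B inhibitors, anticholinergics and amantadine. COMT inhibitors are absent. Against that:

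- OMT subjects continue their current regimen (Sections 5.1.2.1 and 5.5.1.1), and for the non-levodopa classes the list makes no distinction by arm. Read as exhaustive, it would bar the class in OMT too.
- The restart rule covers COMT inhibitors, because they are among the tapered drugs and not among its three exceptions.
- The last paragraph of 5.1.2.2 limits restarts to what Section 5.2.3.2 allows, but the restart rule itself appears in 5.2.3.2.

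One reading fits these texts: stop before LCIG, with restart possible after 28 days. The list is incomplete.

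**5. Size.** Section 5.6.1 says most subjects take other anti-PD drugs, and Section 3.0 says levodopa is often combined with drugs that include COMT inhibitors. Neither gives the number taking the combination tablet at night, which is the group the contradiction concerns. Subjects on a separate COMT inhibitor meet no conflict at entry, because they are plainly told to stop it.

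**The case against.** The best defence is that this is one stray example inside a timing sentence. Table 3, the levodopa list and the stop rule all point to exclusion, and Section 5.2.3 tells sites to contact the sponsor's medical director with any question about concomitant therapy. The consequences are also limited. The analysis sets are ITT and Safety, with no per-protocol set, so calling a use a deviation removes nobody from the primary analysis. Discontinuation for noncompliance is at the investigator's discretion (Section 5.4.1). All medication is recorded, and SAP Section 7.4 already summarises anti-PD drugs by generic name over the 12 weeks.

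Most of this stands, and it makes the point a wording correction. It does not remove the contradiction. A site that sees the tablet named in the section on night dosing has no reason to raise a question.

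A reader might infer more than the documents support:

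- **That the protocol bars COMT inhibitors in the LCIG arm.** No text does so. The class is missing from a list, and the restart rule allows it after 28 days.
- **That obeying Table 3 breaks the unchanged-dose rule.** That clause concerns LC-IR and LC-CR, not the combination tablet.
- **That a separate COMT inhibitor added to infused levodopa-carbidopa recreates a banned combination.** Table 3 bans the product and gives no reason, so this goes beyond the text.
- **That power or the UDysRS difference suffers.** This would need a count of users and an effect per subject, and the documents give neither.

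**Conclusion.** The contradiction over levodopa-carbidopa-entacapone is real and lies in operative dosing rules: Section 5.2.3.4 permits at night what Table 3 prohibits in the same arm. The balance of the text favours the prohibition, so the phrase in 5.2.3.4 is the one to change. The missing COMT-inhibitor entry in the allowed list is a separate, lesser omission that can be reconciled with the rest of the protocol.

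The number affected is not given and could be small. No effect on UDysRS, and no direction, is claimed. The conclusion rests on the wording alone and needs no numerical assumption.

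**What to change.** 1. In Section 5.2.3.4, delete the entacapone product from the examples. Add that subjects who take it at night switch to levodopa-carbidopa or levodopa-benserazide without entacapone before LCIG starts, and that this switch does not breach the unchanged-dose rule.
2. In the allowed-class list of Section 5.2.3.2, add COMT inhibitors: for the OMT group throughout, and for the LCIG group only after the 28-day bar. If the class is meant to stay excluded in the LCIG arm, add it instead to the restart exceptions in the Synopsis, Sections 5.1.2.2 and 5.2.3.2, and SAP Section 4.2, and list it as allowed for OMT only.

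The cost is a few lines of text. No new assessment, analysis or sample-size change follows, and the summary in SAP Section 7.4 already covers reporting of use. The one downside is that a few subjects may have to change their night tablet before LCIG starts.

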5.3 Efficacy and Safety Assessments/Variables

5.3.1 **Efficacy and Safety Measurements Assessed and Flow** Chart

After a subject has signed the Informed Consent, the study activities described in Table 4 will be completed. Subject visit days should ideally match the target clinic visit days. Every attempt should be made to bring the subject back on the target visit day. For all study visits apart from V1 to V3 a \pm 3 days visit window will be allowed. All attempts should be made to return the subject to the planned visit schedule (e.g., if the subject is 2 days late for a Study Visit, the scheduling of the next visit date should be based on the original planned visit date). All scheduled visits are calculated based on Study Day 1 (NJ and/or PEG-J Placement Day for subjects randomized to LCIG Treatment and the day after randomization for subjects randomized to OMT).

ODOVIE Levodopa-Carbidopa Intestinal Gel/Carbidopa Levodopa Enteral Suspension M15-535 Protocol Amendment 1 EudraCT 2016-001403-23

Table 4. Study Activities

		OMT/LCIG	D	LCIG Treatment	ıtment	0	MT/LC	OMT/LCIG Treatment	atment	TCIG I	LCIG Treatment
	V1	V2	V3	V4 NJ/PEG-J	Titration	V5 Wk	V6 Wk	V7 Wk	8A	64	Transition to Commercial
Activity	Screening	Screening	Randomization	Placement D1	Visits	2	4	8	Wk 12/ET	$ m Wk13FU^a$	Visits ^D
Visit Number for OMT/LCIG	V1	V2 ^c (Optional)	V3	V4 ^d		V5	9/	77	8Λ	6Λ	Every 6 and 12 Weeks
Informed Consent ^e	×										
Medical/Neurological/PD History	×		X ^f								
Concomitant Medication (including anti-PD and Dyskinesia medications)	×	×	X	X	X	×	×	×	X	X	X
Anti-PD Medication History	×										
Physical Examination ^g	×	×	X	X		×	×	×	X	X	
Neurological Exam	X	X	X			X	X	X	X	X	
Dermatological Exam ^g	X								X		
GI Exam ^g	X								X		
NJ or PEG-J decision	X										
Nasojejunal Tube Placement/Titration (Optional)				X							
PEG-J Placement Procedure				X							

ODOVIE Levodopa-Carbidopa Intestinal Gel∕Carbidopa Levodopa Enteral Suspension M15-535 Protocol Amendment 1 EudraCT 2016-001403-23

Table 4. Study Activities (Continued)

		OMT/LCIG	S)	LCIG Treatment	ıtment	0	MT/LC	OMT/LCIG Treatment	ıtment	LCIG 1	LCIG Treatment
						VS	9/	V7			Transition to
Activity	V1 Screening	V2 Screening	V3 Randomization	V4 NJ/PEG-J Placement D1	Titration Visits	2 Wk	≱ 4	× ××	V8 Wk 12/ET	V9 Wk 13 FU ^a	Commercial Visits ^b
Radiological Check of Tube Placement				X							
PEG-J Site (Stoma) Check				X^{j}	×					×	
Vital Signs/Weight	X		X	X	×	×	×	×	X	×	X
Height	X										
ECG	X							×	X		
Clinical Labs	X^k		X^k					×	X		
Urine Drug/Alcohol Screen	X										
Special Laboratory Tests	X		X					×	X		X
Pregnancy Test ^m	X			X					X		
Adverse Events	X	X	X	X	X	X	X	X	X	X	X
Product Complaints				X	X	X	×	×	X	X	X
Dose Titration Diary				X	×						
Subject Dosing Diary Completion					X	X	X	X	X		
PD Diary training and concordance evaluation	X										
PD Diary ^o			X			X	×	X	X		

Table 4. Study Activities (Continued)

Activity V1 V2 V3 V4M/PEG-J Tirration Tirration Wish Assignment Wish Subject and Carcegives) V2 V3 V4 V6 V7 V8 V8 V8 V8 Common Activity LCIG System and Pump Carcegives) Training (Subject and Carcegives) X 		OMT/LCI	10	LCIG Treatment	tment	0	MT/LC	OMT/LCIG Treatment	ıtment	TCIG T	LCIG Treatment	OMT/LCI	10	LCIG Treatment	tment	0	MT/LC	OMT/LCIG Treatment	ıtment	TCIG T	LCIG Treatment
yearm and Pump (system and Pump (system) an	:	ĪA	. V2	V3	V4 NJ/PEG-J	Titration	V5 Wk	V6 Wk	V7 Wk	8/	60	Transition to
ystem and Pump (c) g (Subject and Pump (c) triation** Tritation** Dug Prescription Tritation** Dug Prescription And	Activity	Screening	Screening	Randomization	Placement D1	Visits	2	4	œ	Wk 12/ET	Wk 13 FU"	Visits
TirrationPrough Turning Programment Angle Prescription (LCIG treatment Angle) X	LCIG System and Pump Training (Subject and Caregiver)			×	×							
Dug Prescription (LCIG treatment mily) X	LCIG Titration ^p				X	X						
al of PEG.1** Assettes Dispensed X Attacks X XI A X X X X X X X X X X X X	Study Drug Prescription Record (LCIG treatment group only)				X	X	X	×	X	X	X	
Cassettes Dispensed X	Removal of PEG-J ^a									X		
Cassettes Returned X	LCIG Cassettes Dispensed				X		X	×	X	X	X	X
Attacks X </td LCIG Cassettes Returned						X	X	X	X	X	X	LCIG Cassettes Returned						X	X	X	X	X	X
Attacks X </td MMSE	X		MMSE	X										
Si	Sleep Attacks Questionnaire ^q	X	X	X			Х	Х	Х	X	X	
Ss	C-SSRS ^r	X	X	X	X		X	X	X	X	X	X
SSs X	MIDI	X	X	X			X	X	X	X	X	X
S II and III [†] Su X X X X X X X X X X X X X	$\mathrm{UDysRS}^{\mathrm{s}}$			X			X	X	X	X		
x x x x x x x x x x x x x x x x x x x	UPDRS II and III ^t	X		X			X	X	X	X		
	mAIMS ^u			X			X	X	X	X		
	PDQ-8			X					X	X		
	CGI-C						X	X	X	X		

Table 4. Study Activities (Continued)

		OMT/LCIG	B	LCIG Treatment	ıtment	[0	MT/LC	OMT/LCIG Treatment	atment	TCIG T	LCIG Treatment
	VI	V2	V3	V4 NJ/PEG-J Titration	Titration	V5 Wk	V6 Wk	V7 Wk	8/	6/	Transition to Commercial
Activity	Screening	Screening Screening	Randomization	Placement D1	Visits		4	∞	Wk 12/ET Wk 13 FU ^a	Wk 13 FU ^a	Visits ^b
S-I9O			X								
King's PD Pain Scale			X				X	X	X		

V = Visit; D = Day; FU = Follow-Up; Wk = Week

Applicable only to LCIG subjects who prematurely discontinue LCIG treatment, or complete LCIG study treatment but will not transition to commercial LCIG. a. Applicable only to LCIG subjects who complete LCIG study treatment and will transition to commercial LCIG. Subjects will return every 6 weeks to return used LCIG cassettes and be dispensed cassettes. Safety assessments will be completed every 12 weeks until subjects' transition to commercial LCIG. Visit 2 is optional and is based on the Investigator's discretion of individual subject need during stabilization of anti-PD medications and medications to treat dyskinesia.

Visit 4 for LCIG Treatment (LCIG) group only.

d.

Study-related assessments, procedures or activities cannot occur prior to subject completing signed informed consent process. e.

f. Update Medical/Neurological/PD History with any findings from Labs, Dermatologists, etc.

At Screening Visit 1 and Randomization Visit 3 a full physical examination will be performed. Symptom-driven physical examinations will be performed at subsequent visits. Prior to Visit 3, the Investigator and GI/surgeon or interventional radiologist, or their designated qualified personnel will thoroughly evaluate the subject's risk of undergoing PEG-J procedure. The dermatological exam will be performed prior to Visit 3 and Week 12/ET visit. If a suspicious lesion is present, a biopsy should be obtained for proper diagnosis and confirmation that lesion does not meet exclusion criteria before the subject is randomized.

time to titration via NJ and PEG-J should not exceed 14 days. Alternatively, subjects may proceed directly to placement of PEG-J if deemed appropriate by Investigator. The should not last longer than 7 days. Following the NJ test phase, a PEG-J will be performed by a gastroenterologist proceduralist, surgeon or interventional radiologist. Total For subjects randomized to LCIG treatment, a temporary NJ tube may be used to optimize the dose of LCIG before treatment with a PEG-J is started. The NJ test phase number of days to titrate will vary for each subject. þ.

LCIG treatment group only. Radiological check of NJ and PEG-J to determine correct location should occur prior to LCIG infusion initiation and prior to restart of LCIG oost PEG-J placement. Additional checks can be done at any time during treatment if indicated for worsening of Parkinsonian symptoms not responsive to extra doses.

PEG-J site, stoma check will be done within 24 hours of PEG-J placement and anytime from Day 2 to 7 post PEG-J.

PT/PTT will be performed only at Screening Visit 1.

Table 4. Study Activities (Continued)

- Special labs to detect vitamin deficiencies, listed in Table 5, will be performed at the times indicated in Table 4. If at any time during the study a subject displays symptoms of polyneuropathy, the Investigator must perform this lab panel and any other assessment that the Investigator feels is appropriate for further evaluation of polyneuropathy symptoms. Thyroid function tests will be done at Screening Visit 1 only.
- All females of childbearing potential must have a serum pregnancy test performed at Screening Visit 1 and Premature Discontinuation/End of Study. Additional testing may be required per local regulations. A negative urine pregnancy test result is required prior to the NJ and/or PEG-J placement procedure and any radiological procedures. ij.
- hourly until the dose is optimized and then once AM and once PM it will be completed until the subject is discharged. All adjustments can be recorded on the Dose Titration Diary allowing the Investigator to appropriately adjust, if needed, the following day's morning dose, continuous infusion rate and extra dose until the subject is optimized. While the subject is in the hospital, the study staff may use the Dose Titration Diary as a tool to achieve dose optimization. In the event it is used it should be completed ij.
- The Subject Dosing Diary and the Parkinson's Disease Diary will be completed by the subjects or their caregivers for the 3 consecutive days prior to each visit. ö
- It is up to the discretion of the Investigator to determine how many titration days are necessary to obtain optimal clinical response.

р.

- The Sleep Attacks Questionnaire will be used to screen for sleep attacks. Results should be recorded in source but will not be entered in the clinical database. 4
- The "Baseline/Screening" C-SSRS will be the first assessment scale administered to the subject. At each subsequent visit, the "Since Last Visit" C-SSRS scale should be administered.
- The subject's expected time of peak dose dyskinesia should be determined during screening and the UDysRS should be administered at this time throughout the study ò
- morning prior to the subject taking their first daily dose of anti-PD medication. At a minimum a subject should be 8 hours without anti-PD medication before the UPDRS is completed. The best "On" time rating should be done approximately 1 to 2 hours post any morning dose of study drug or PD medications but prior to lunch. If possible, the UPDRS should be done at the same time of day throughout the trial. The "Off" time UPDRS Part III will only be done during Screening; all other UPDRS assessments will During Visit 1 the UPDRS Part III will be done during practically defined "Off" time and best "On" time. The practically defined "Off" time UPDRS will be done in the
- The mAIMS should be completed following the UDysRS at the subject's expected time of peak dose dyskinesia. 'n.

All applicable clinical, safety, health outcome and cognition assessments will be administered only by individuals qualified by the Sponsor. Note:

5.3.1.1 **Study Procedures**

The study procedures outlined in Table 4 are discussed in this section, with the exception of the collection of adverse event information and product complaints (Section 6.0).

Due to the length of assessments on Visit 1, assessments may be performed over multiple days.

Informed Consent

Voluntary written informed consent must be obtained from each subject (and if appropriate, their caregiver) by the Investigator prior to performing any study-related procedures. Consenting will be performed according to local regulations.

Subject Medical and Neurological History

A complete medical history, including alcohol, drug, tobacco and nicotine-containing product use histories will be taken at the time indicated in Table 4. Additionally, chronic disorders (e.g., diabetes and hay fever) that began prior to Screening and are still present at Screening should be recorded on the Medical History Form. The Medical History obtained at V1 will serve as the baseline for clinical assessment. All psychiatric, neurological, behavioral and/or cognitive diagnosis should be reported. Updates should be made to the Medical/Neurological/PD History with any findings from Labs, Dermatologists, etc.

Mini-Mental State Examination (MMSE)

The MMSE²⁸ is a brief, 30-point questionnaire, administered by a trained rater, which provides a quantitative measure of cognitive mental status in adults and is widely used to screen for cognitive impairment and to estimate the severity of cognitive impairment at a given point in time, to follow the course of cognitive changes in a subject over time, and to document response to treatment. In this study, MMSE will be used to screen for cognitive impairment. The subject must have a score ≥ 24 at Screening Visit 1 to be

Chock Levodopa-Carbidopa Intestinal Gel/Carbidopa Levodopa Enteral Suspension M15-535 Protocol Amendment 1 EudraCT 2016-001403-23

eligible for study participation. Lower scores indicate greater impairment. The MMSE will be administered at Visit 1 as indicated in Table 4.

Sleep Attacks Questionnaire

To prospectively monitor for possible development of sleep attacks, the subject will be evaluated for sleep attacks at the times indicated in Table 4. The subject will be asked the following Sleep Attack Assessment questions:

Since your last visit or last time this question was asked, have you experienced any events in which you fell asleep suddenly or unexpectedly, including while engaged in some activity (e.g., eating/drinking, speaking, or driving) or at rest, without any previous warning of sleepiness (e.g., feeling tired)?

- If yes, what specifically happened?
- How many times did you experience such events?
- What were you doing at the time of each event?
- Prior to each event did you experience any sleepiness or drowsiness? If yes, please explain/clarify.
- How long did each event last?
- Did you suffer any "bad" outcome/problem from each falling asleep event?

During the Screening Period, subjects should be asked to answer these questions based on their experiences during the 3 months prior to Screening Visit 1. During the Screening Period, if the subject is currently or has been recently experiencing sleep attacks, they will be excluded from participation in the study and referred for appropriate follow-up care if the Investigator feels these are clinically significant. The assessment of Sleep Attacks completed at the Screening Visit 1 will serve as baseline for clinical assessment.

EudraCT 2016-001403-23

Physical Examination

At Screening V1, V2 (optional visit) and Randomization V3 a full physical examination will be performed. Symptom-driven physical examinations will be performed at subsequent visits.

Neurological Examination

A Neurological Examination including light touch and pinprick sensation, vibratory sensation, deep tendon reflexes, and strength assessments will be performed at the times indicated in Table 4. The Neurological Examination should be bilateral and be done during the subject's "On" time.

Any abnormalities or symptoms identified at Visits 1, 2 and 3 will not be recorded as adverse events but will be recorded in Medical History eCRF. Any new abnormalities or symptoms that change in severity or frequency following randomization for the OMT group and the first dose of IP for the LCIG treatment group will be recorded as adverse events.

The Neurological Examination will assess:

- Cranial nerves assessment of cranial nerves II XII, including fundoscopic examination
- Motor system assessment of tone, strength and abnormal movements
- Sensory system including light touch, pinprick, joint position and vibratory sense
- Reflexes assessment of deep tendon reflexes and plantar responses (Babinski
- Coordination assessment of upper and lower extremities
- Gait assessment of base and tandem gait

The Neurological Examination performed at Visit 1, will serve as baseline for clinical assessment.

Dermatological Assessment

A comprehensive assessment by an experienced dermatologist for the presence of any suspicious skin lesions and subsequent evaluation for melanoma will be performed prior to V3 and at Week 12/Premature Discontinuation. If a suspicious lesion is present, a biopsy should be obtained for proper diagnosis and confirmation that lesion does not meet exclusion criteria.

Positive screens will be exclusionary.

GI Examination

On or prior to V2, the Investigator and GI/surgeon will thoroughly evaluate the subject's risk of undergoing PEG-J procedure.

NJ and/or PEG-J Placement (LCIG Treatment Group Only)

For subjects randomized to LCIG, a temporary NJ tube may be used to optimize the dose of LCIG before treatment with a PEG-J is started. The NJ test phase should not last longer than 7 days. Following the NJ test phase, a PEG-J will be performed by a gastroenterologist proceduralist, surgeon or interventional radiologist. Total time to titration via NJ and PEG-J should not exceed 14 days. Alternatively, subjects may proceed directly to placement of the PEG-J if deemed appropriate by the Investigator. Total time to titration via the NJ and PEG-J should not exceed 14 days. The number of days to titrate will vary for each subject.

Radiological Check of Tube Placement (LCIG Treatment Group Only)

Radiological check of NJ and PEG-J to determine correct location should occur prior to LCIG infusion initiation and prior to restart of LCIG treatment post PEG-J placement. It can also be done at any time during treatment if indicated for worsening of Parkinsonian symptoms or non-responsiveness to extra doses.

PEG-Site (Stoma) Check (LCIG Treatment Group Only)

Following the PEG-J placement, site personnel will review proper after-care instructions and checking of the stoma instructions with the subject and/or care-giver as provided in the patient care materials/booklets.

After the initial PEG-J procedure, the PEG-J and stoma must be inspected by a gastroenterologist proceduralist, surgeon or interventional radiologist (preferably the physician who placed the PEG-J), or their designated qualified personnel within 24 hours and 2-7 days post PEG-J procedure.

Vital Signs/Weight

Body temperature, orthostatic vital signs and weight will be performed at the times indicated in Table 4. All systolic and diastolic blood pressure and pulse rate measurements are to be measured orthostatically. Orthostatic systolic and diastolic blood pressure and pulse rate are to be measured while the subject is supine (after 3 to 5 minutes) and standing (after 2 minutes). Study staff should make efforts to measure with the same arm and method including recording of arm and method in the subject's source documentation.

Vital signs will include body weight will be measured at the times indicated in Table 4. The subject will wear lightweight clothing and no shoes during weighing.

Height

